8.3.8 Hy's law

Cases where a subject shows elevation in liver biochemistry may require further evaluation and occurrences of AST or ALT $\geq 3\times$ ULN together with total bilirubin $\geq 2\times$ ULN may need to be reported as SAEs. Please refer to Appendix E for further instruction on cases of increases in liver biochemistry and evaluation of Hy's Law.

8.3.9 Disease-under study (DUS)

Symptoms of DUS are those which might be expected to occur as a direct result of advanced ovarian or metastatic breast cancer. The symptoms include:

- 1) Abdominal bloating, indigestion or nausea.
- 2) Changes in appetite, such as a loss of appetite or feeling full sooner.
- 3) Pressure in the pelvis or lower back.
- 4) A more frequent or urgent need to urinate and/or constipation.
- 5) Changes in bowel movements.
- 6) Increased abdominal girth.
- 7) Tiredness or low energy.
- 8) Changes in menstruation.
- 9) constant back, bone, or joint pain.
- 10) numbness or weakness anywhere in your body.
- 11) a constant dry cough.
- 12) difficulty breathing.
- 13) shortness of breath.
- 14) chest pain.

Events which are unequivocally due to disease under study should not be reported as an AE during the study unless they meet SAE criteria or lead to discontinuation of the study drug. All the events occurring at the Indian sites that meet the criteria for seriousness will be reported expeditiously as SAEs per local regulatory requirements to the Indian regulatory authority and the concerned ethics committees.

8.3.10 Disease progression

Disease progression can be considered as a worsening of a subject's condition attributable to the disease for which the study drug is being studied. It may be an increase in the severity of the disease under study and/or increases in the symptoms of the disease. The development of new or progression of existing metastasis to the primary cancer under study should be considered as disease progression and not an AE. Events that are unequivocally due to disease progression should not be reported as an AE during the study. All the events occurring at the Indian sites that meet the

criteria for seriousness will be reported expeditiously as SAEs per local regulatory requirements to the Indian regulatory authority and the concerned ethics committees.

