The approval for olaparib in ovarian cancer is based on Study 19 (n = 265), Study 42 (n = 137) and SOLO2 (n = 295). Study 19, a phase II study, which included patients irrespective of their BRCA status, showed a significant progression free survival (PFS) benefit (8.4 vs 4.8 months) over placebo with a hazard ratio of 0.35, p <0.0001 (Ledermann et al., 2012). There is now long term safety and efficacy data of the patients enrolled in Study 19 with 15 patients (11%) on the study drug for >6 years which included an equal proportion of gBRCAm as well as non – BRCA mutated patients (Gourley et al., 2017). In Study 19 (dose of olaparib used in the study was 400 mg BD in Capsule formulation), common grade 3 or worse adverse events in the olaparib group were fatigue (8%) and anaemia (6%). 22 % patients in the olaparib group reported serious adverse events.(Ledermann JA , et al, 2016) The phase III SOLO2 study which included only gBRCAm patients with ovarian cancer in the maintenance management of ovarian cancer, showed a significant PFS benefit over placebo (19.1 vs 5.5 months; HR of 0.30, p <0.0001) (Pujade-Lauraine et al., 2017). In the SOLO – 2 study (dose of olaparib used in the study was 300 mg BD in tablet formulation), serious adverse events were experienced by 18 % patients in the olaparib group compared to 8 % patients in the placebo group. The most common in the olaparib group were anaemia (4 % patients), abdominal pain (2% patients), and intestinal obstruction (2 % patients)

(Pujade-Lauraine et al., 2017). In the third-line or later treatment indication of olaparib, the approval is based on the results of the phase II study 42 (n = 137), which, in gBRCAm patients showed an ORR of 34% (Domchek et al., 2016; Matulonis et al., 2016). In Study 42, Grade ≥ 3 AE's were observed in 55 % of the patients with the commonest ones being anaemia (20 %), abdominal pain (8 %) and fatigue (7 %). (Domchek et al., 2016)

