3. OBJECTIVES AND ENDPOINTS

Table 3 Study objectives

Primary objective:	Endpoint/variable:
To assess the safety of olaparib in Indian subjects with: 
platinum sensitive relapsed ovarian cancer who are in complete or partial response following platinum-based chemotherapy, andHER - 2 negative metastatic breast cancer with germline BRCA1/2 mutation.	Number, frequency and proportion of subjects with adverse events (AEs) and serious adverse events (SAEs). The safety variables to be analysed include AEs, clinical laboratory tests (haematology and chemistry), physical examination results, vital parameters, World Health Organization (WHO) performance status (PS), and deaths as observed by participating physician.

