7.1 Discontinuation of study treatment

Subjects may be discontinued from olaparib in the following situations. Note that discontinuation from study treatment is NOT the same thing as a complete withdrawal from the study

- Disease Progression: Disease progression can be considered as a worsening of a subject's condition attributable to the disease for which the study drug is being studied. It may be an increase in the severity of the disease under study (DUS) and/or increases in the signs and symptoms of the cancer. The development of new, or progression of existing metastasis to the primary cancer under study should be considered as disease progression and not an AE (if the progression was 'as expected'). Events, which are unequivocally due to disease progression, should not be reported as an AE during the study. All the events occurring at the Indian sites that meet the criteria for seriousness will be reported expeditiously as SAEs per local regulatory requirements to the Indian regulatory authority and the concerned ethics committees. In this study, disease progression shall be determined by the investigator as per the guidelines currently being followed by the site for the indication in question. Progression of disease assessed radiographically should occur in comparison to baseline imaging obtained during screening.

- Adverse Event (including laboratory abnormality or intercurrent illness) which, in the opinion of the investigator, indicates that continued participation in the study is not in the best interest of the subject
- The subject (or the subject's legally acceptable representative) withdraws consent for administration of study drug
- ILD/Pneumonitis
- Acute myeloid leukemia/Myelodysplastic syndrome or other de novo malignancy requiring active treatment
- Pregnancy
- Any adverse event deemed to be related to olaparib that requires a dose hold of more than 21 days will result in permanent discontinuation of olaparib.
- Grade 3 or higher adverse reaction that does not improve to Grade 0-2 after withholding for up to 3 weeks
- Severe non-compliance with the Clinical Study Protocol
- The patient has a confirmed positive serum pregnancy test

See the SoA for data to be collected at the time of treatment discontinuation and follow-up and for any further evaluations that need to be completed.

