8.3.7 Adverse events based on examinations and tests

The results from the Clinical Study Protocol mandated laboratory tests and vital signs will be summarised in the CSR. Deterioration as compared to baseline in protocol-mandated laboratory values, vital signs as in section 8.2 should therefore only be reported as AEs if they fulfil any of the SAE criteria or are the reason for discontinuation of treatment with the study drug.

If deterioration in a laboratory value/vital sign is associated with clinical signs and symptoms, the sign or symptom will be reported as an AE and the associated laboratory result/vital sign will be considered as additional information. Wherever possible the reporting Investigator uses the clinical, rather than the laboratory term (e.g., anaemia versus low haemoglobin value). In the absence of clinical signs or symptoms, clinically relevant deteriorations in non-mandated parameters should be reported as AE(s).

Deterioration of a laboratory value, which is unequivocally due to disease progression, should not be reported as an AE/SAE.

Any new or aggravated clinically relevant abnormal medical finding at a physical examination as compared with the baseline assessment will be reported as an AE unless unequivocally related to the disease under study, see sections 8.3.9 and 8.3.10.

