Appendix B Adverse event definitions and additional safety information

B 1 Definition of adverse events

An adverse event is the development of any untoward medical occurrence in a subject or clinical study subject administered a medicinal product and which does not necessarily have a causal relationship with this treatment. An AE can therefore be any unfavourable and unintended sign (e.g. an abnormal laboratory finding), symptom (for example nausea, chest pain), or disease temporally associated with the use of a medicinal product, whether or not considered related to the medicinal product.

The term AE is used to include both serious and non-serious AEs and can include a deterioration of a pre-existing medical occurrence. An AE may occur at any time, including run-in or washout periods, even if no Study treatment has been administered.

B 2 Definitions of serious adverse event

A serious adverse event is an AE occurring during any study phase (i.e., run-in, treatment, washout, follow-up), that fulfils one or more of the following criteria:

- Results in death
- Is immediately life-threatening
- Requires in-subject hospitalisation or prolongation of existing hospitalisation
- Results in persistent or significant disability or incapacity.
- Results in a congenital abnormality or a birth defect
- Is an important medical event that may jeopardise the subject or may require medical treatment to prevent one of the outcomes listed above.

B 3 Life threatening

'Life-threatening' means that the subject was at immediate risk of death from the AE as it occurred, or it is suspected that use or continued use of the product would result in the subject's death. 'Life-threatening' does not mean that had an AE occurred in a more severe form it might have caused death (e.g., hepatitis that resolved without hepatic failure).

B 4 Hospitalisation

Outpatient treatment in an emergency room is not in itself a serious AE, although the reasons for it may be (e.g., bronchospasm, laryngeal oedema). Hospital admissions and/or surgical operations planned before or during a study are not considered AEs if the illness or disease existed before the subject was enrolled in the study, provided that it did not deteriorate in an unexpected way during the study.

B 5 Important medical event or medical treatment

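### The rules for recording progression-related events conflict, so part of the primary AE and SAE proportions depends on which section a site follows

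*Protocol*

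**What the plan says.** Section 3 (Table 3) sets the primary endpoint as "Number, frequency and proportion of subjects with adverse events (AEs) and serious adverse events (SAEs"), and names deaths among the safety variables. Five places then govern whether a progression-related event reaches that count.

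- **8.3.10:** "Events that are unequivocally due to disease progression should not be reported as an AE during the study". No exception is attached. The next sentence says that all events meeting seriousness criteria are reported as SAEs.
- **7.1:** repeats both sentences, but qualifies the one on metastases: new or progressing metastasis "should be considered as disease progression and not an AE (if the progression was 'as expected"). Section 8.3.10 has no such qualifier.
- **8.3.9 (disease-under-study symptoms):** such events "should not be reported as an AE during the study unless they meet SAE criteria or lead to discontinuation of the study drug". It then adds: "All the events occurring at the Indian sites that meet the criteria for seriousness will be reported expeditiously as SAEs per local regulatory requirements".
- **8.3.7:** "Deterioration of a laboratory value, which is unequivocally due to disease progression, should not be reported as an AE/SAE". No exception is made for serious cases.
- **Appendix B 2:** "A serious adverse event is an AE occurring during any study phase", so an event that is not an AE cannot be an SAE.

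Section 8.4.1 has all SAEs recorded in the CRF, and the electronic alert to the sponsor starts when a site marks an AE as serious. Section 9.4.2 includes AEs up to 28 days after the last dose in the summaries.

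**The concern.** Read literally, a hospitalisation for progression is both not an AE and an SAE, although every SAE is by definition an AE. A serious laboratory change due to progression is an SAE under one section and neither AE nor SAE under another. A worsening cancer symptom that leads to stopping the drug is an AE under 8.3.9 and not one under 8.3.10.

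These are collection rules and they feed the primary endpoint directly. An analysis plan can choose how to tabulate what was entered, but it cannot recover events that a site left out because it followed the exclusion. Progression itself leads to discontinuation, and the 28 days after the last dose count in the AE summaries, so many of these events would fall inside the reporting window. The protocol does not say whether they belong in the primary proportions.

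**Working it through.** **Step 1: the rules side by side.**

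| Event | 7.1 and 8.3.10 | 8.3.9 | 8.3.7 |
|---|---|---|---|
| Hospitalisation or death from progression | Not an AE (exclusion), then SAE (next sentence) | SAE | Not addressed |
| Serious, laboratory-only deterioration due to progression | SAE by the seriousness sentence | SAE by the same sentence | Neither AE nor SAE |
| Non-serious cancer symptom leading to discontinuation | Not an AE | AE | Not addressed |
| Non-serious metastatic progression judged not as expected | Open in 7.1, not an AE in 8.3.10 | Not addressed | Not addressed |
| Other non-serious progression event | Not an AE | Not an AE | Not an AE (laboratory values) |

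The third row matters because 8.3.10 includes increasing symptoms of the disease in its description of progression, so it overlaps with 8.3.9. Section 8.3.7 does write an exception for serious events and discontinuations for laboratory deterioration in general, but its sentence on progression drops it.

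**Step 2: the protocol's own figure.** The only planning figure is about 190 subjects for a 40% incidence within 7 points (9.2): 1.96² × 0.40 × 0.60 / 0.07² = 188.2, rounded up to 189. It reproduces, is not in dispute, and concerns grade 3 or higher labelled AEs, not SAEs.

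**Step 3: an illustrative upper bound on the SAE proportion.** Inputs from the protocol:

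- 160 ovarian and 40 breast subjects (9.2).
- A 182-day Treatment Phase (4.1), so 182 / 30.4375 = 5.98 months.
- Median PFS of 19.1 or 8.4 months for ovarian cancer (4.2) and 7 months for breast cancer (2.1).
- An earlier ovarian tablet trial in which "serious adverse events were experienced by 18 % patients in the olaparib group" (2.1).

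Assumptions that are not in the protocol: exponential PFS, 10% to 25% of those progressing have a serious event due only to progression, and none of these has another SAE.

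- Progressed or dead by Day 182 = 1 − 2^(−5.98/median): 19.5% (19.1 months), 38.9% (8.4 months), 44.7% (7 months).
- Low: 160 × 0.195 + 40 × 0.447 = 49 subjects. High: 160 × 0.389 + 40 × 0.447 = 80 subjects.
- Serious progression-only events: 10% of 49 ≈ 5 and 25% of 80 = 20 subjects, which is 2.5 to 10 points on 200.
- For scale, the 95% half-width at 18% and n = 200 is 1.96 × √(0.18 × 0.82 / 200) = 5.3 points, about 11 subjects.

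With an assumed serious share of 5% to 30% instead, the range becomes 1.2 to 12.0 points, so the result is driven by the assumption. In both cases the calculation compares counting every such event with counting none. It does not estimate how far sites would actually differ.

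**The case against.** The strongest reply is that the sections agree on the events that matter most. Sections 7.1, 8.3.9 and 8.3.10 all carry the same seriousness sentence, and in 7.1 and 8.3.10 it directly follows the exclusion. The natural reading is that non-serious progression events are not AEs and serious ones are SAEs. Section 8.3.9 says so outright for disease symptoms, and 8.4.1 sends every SAE to the CRF. Section 8.3.7 covers laboratory values only, and where symptoms accompany the change, the symptom is what gets reported. Section 8.3.4 already collects the verbatim term, the reason for seriousness and the probable cause of death, and deaths are a safety variable in their own right.

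Much of this stands. Most sites would probably record a progression hospitalisation or death as an SAE, and many recorded cases could be recognised from existing fields. What does not fall away is the written conflict on serious laboratory-only events and on symptoms leading to discontinuation, and the risk that some sites apply the flat exclusion. Fields on a form cannot identify an event that was never entered, and for non-fatal events the verbatim term is an uncertain guide to progression.

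A reader might infer two stronger things. One is that the SAE proportion as a whole loses its meaning. The shared seriousness sentence and 8.4.1 do not support that. The other is that counting progression makes olaparib look worse than in trials that leave it out. The protocol does not say how earlier trials, including the one with 18% SAEs, treated progression, and 2.2 rules out statistical comparison with the global trials.

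**Conclusion.** The conflict is real and should be repaired, because it sits in the collection rules for the primary AE and SAE proportions. Its likely reach is limited to three groups: serious laboratory-only progression events, progression symptoms leading to discontinuation, and events at sites that follow the exclusion literally. The size of that divergence cannot be derived from the document.

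The 2.5 to 10 point figure is only an illustrative upper bound for all-versus-none counting. It rests on exponential PFS, an assumed serious share of 10% to 25%, no overlap with other SAEs, and medians from other trials (the 8.4 months comes from a capsule study at 400 mg BD). It shows that the rule could matter against a sampling half-width of about 5 points, not that it will. Counting serious progression events as SAEs is itself defensible in a single-arm regulatory safety study. The fault is that the protocol does not say so consistently.

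**What to change.** Reconcile 7.1, 8.3.7, 8.3.9 and 8.3.10 into one explicit recording rule. It should state whether serious progression events, including laboratory-only ones, and progression symptoms leading to discontinuation are entered in the CRF as SAEs or AEs. It should either keep the as-expected qualifier in both 7.1 and 8.3.10 or remove it from 7.1, and it should fit the definition in Appendix B 2. Expedited reporting to the authority and ethics committees stays unchanged.

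Add a progression flag to the AE/SAE form, and report the SAE and fatal-event proportions both with and without flagged events. Which of the two tables leads can be left to the analysis plan.

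The cost is one CRF field, aligned wording in four sections and one extra table.

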8.4 Safety reporting and medical management

8.4.1 Reporting of serious adverse events

All SAEs have to be reported, whether or not considered causally related to the study drug, or to the study procedure(s). All SAEs will be recorded in the CRF.

If any SAE occurs in the course of the study, then Investigators or other site personnel inform the appropriate AstraZeneca representatives within one day i.e., immediately but **no later than 24 hours** of when he or she becomes aware of it.

The designated AstraZeneca representative works with the Investigator to ensure that all the necessary information is provided to the AstraZeneca Patient Safety data entry site **within 1 calendar day** of initial receipt for fatal and life-threatening events and **within 5 calendar days** of initial receipt for all other SAEs.

For fatal or life-threatening adverse events where important or relevant information is missing, active follow-up is undertaken immediately. Investigators or other site personnel inform AstraZeneca representatives of any follow-up information on a previously reported SAE within one calendar day i.e., immediately but **no later than 24 hours** of when he or she becomes aware of it.

Once the Investigators or other site personnel indicate an AE is serious in the EDC system, an automated email alert is sent to the designated AstraZeneca representative.

If the EDC system is not available, then the Investigator or other study site staff reports a SAE to the appropriate AstraZeneca representative by telephone.

The AstraZeneca representative will advise the Investigator/study site staff how to proceed.

Investigators or other site personnel send relevant CRF modules by fax to the designated AstraZeneca representative.

For further guidance on the definition of a SAE, see Appendix B of the Clinical Study Protocol.

8.4.2 Pregnancy

All pregnancies and outcomes of pregnancy should be reported to AstraZeneca except for:

- If the pregnancy is discovered before the study subject has received any study drug

If a pregnancy is reported, the investigator should inform the sponsor within 24 hours of learning of the pregnancy.

Abnormal pregnancy outcomes (eg, spontaneous abortion, foetal death, stillbirth, congenital anomalies, ectopic pregnancy) are considered SAEs.

8.4.2.1 Maternal exposure

If a subject becomes pregnant during the course of the study, the study drug olaparib should be discontinued immediately.

Pregnancy itself is not regarded as an adverse event unless there is a suspicion that the study drug under study may have interfered with the effectiveness of a contraceptive medication. Congenital abnormalities/birth defects and spontaneous miscarriages should be reported and handled as SAEs. Elective abortions without complications should not be handled as AEs. The outcome of all pregnancies (spontaneous miscarriage, elective termination, ectopic pregnancy, normal birth or congenital abnormality) should be followed up and documented even if the subject was discontinued from the study.

If any pregnancy occurs during the course of the study, then the Investigator or other site personnel informs the appropriate AstraZeneca representatives within 1 day i.e., immediately but **no later than 24 hours** of when he or she becomes aware of it.

The designated AstraZeneca representative works with the Investigator to ensure that all relevant information is provided to the AstraZeneca Patient Safety data entry site within 1 or 5 calendar days for SAEs (see Section 9.2.5) and within 30 days for all other pregnancies.

The same timelines apply when outcome information is available.

<<When the CRF module is used include the following: The PREGREP module in the CRF is used to report the pregnancy and the PREGOUT is used to report the outcome of the pregnancy.>>

8.4.3 Overdose

For this study, any dose of olaparib greater than 300 mg BD within 24 hours will be considered an overdose.

AstraZeneca does not recommend specific treatment for an overdose.

- An overdose with associated AEs is recorded as the AE diagnosis/symptoms on the relevant AE modules in the CRF and on the Overdose CRF module.
- An overdose without associated symptoms is only reported on the Overdose CRF module

If an overdose on an AstraZeneca study drug occurs in the course of the study, then the Investigator or other site personnel inform appropriate AstraZeneca representatives immediately, or **no later than 24 hours** of when he or she becomes aware of it.

The designated AstraZeneca representative works with the Investigator to ensure that all relevant information is provided to the AstraZeneca Patient Safety data entry site.

For overdoses associated with a SAE, the standard reporting timelines apply, see Section 8.3.2. For other overdoses, reporting must occur within 30 days.

